1.2 Synopsis

International Coordinating Investigator

PPD

Fondazione IRCCS Policlinico San Matteo
[name]
Pavia, Italy

Protocol title:

A Phase II, Open-label, Multicenter, International Study of Durvalumab Following Radiation Therapy in Patients with Stage III, Unresectable Non-Small Cell Lung Cancer Who Are Ineligible for Chemotherapy (DUART)

Rationale:

Durvalumab (MEDI4736) is a human monoclonal antibody (mAb) of the immunoglobulin G (IgG) 1 kappa subclass that blocks the interaction of programmed cell death ligand 1 (PD-L1) (but not programmed cell death ligand-2) with programmed cell death receptor (PD-1) on T cells and cluster of differentiation (CD)80 (B7.1) on immune cells. It is being developed by AstraZeneca/MedImmune for use in the treatment of cancer. Results of early studies with durvalumab in advanced cancers are consistent with a class effect of early and sustained tumor control that has been observed previously with other inhibitors of the immune-checkpoint pathway. As radiation therapy is known to upregulate PD-L1, using durvalumab subsequent to radiation therapy could potentially provide better clinical outcomes in this population. Results from the PACIFIC Study in patients with Stage III unresectable non-small cell lung cancer (NSCLC) following concurrent chemoradiation therapy (cCRT) demonstrated a significant increase in median progression-free survival (PFS) and a significant increase in overall survival (OS) among patients who received durvalumab compared with placebo. Safety results from this study demonstrated that durvalumab monotherapy was well tolerated and had a manageable safety profile in this patient population. However, many patients with Stage III unresectable NSCLC are unable to undergo chemotherapy; these patients are therefore faced with fewer treatment options. The main goal of this study is to evaluate the safety and tolerability of maintenance treatment with durvalumab following radiation therapy in this population.

Objective	Endpoint/variable
Primary objective	
To assess the safety and tolerability profile of durvalumab as defined by Grade 3 and Grade 4 PRAEs within 6 months from the initiation of durvalumab treatment	Grade 3 and Grade 4 PRAEs
Secondary objectives	
To assess the efficacy of durvalumab treatment in terms of PFS and OS	Median PFS according to RECIST 1.1 as assessed by the Investigator PFS6 and PFS12 according to RECIST 1.1 as assessed by the Investigator Median OS and OS12
To further assess the efficacy of durvalumab treatment in terms of ORR and DoR	ORR according to RECIST 1.1 as assessed by the Investigator DoR according to RECIST 1.1 as assessed by the Investigator
To assess the efficacy of durvalumab treatment in terms of lung cancer mortality	Lung cancer mortality
To further assess the safety and tolerability profile of durvalumab treatment, including all AEs	AEs, SAEs, AESIs, imAEs, physical examinations, vital signs including BP, pulse, ECGs, and laboratory findings including clinical chemistry, hematology, and urinalysis
Exploratory objectives	
CCI	CCI

Objective	Endpoint/variable
CC1 [REDACTED]	CC1 [REDACTED]

AE = Adverse event; AESI = Adverse event of special interest; BP = blood pressure; DoR = Duration of response; CTCAE = Common Terminology Criteria for Adverse Event; CCI
ECG = Electrocardiogram; CCI
CC1 [REDACTED] d
CC1 [REDACTED];
imAE = Immune-mediated adverse events; IP = Investigational product; NCI = National Cancer Institute; ORR = Objective response rate; OS = Overall survival; OS12 = Proportion of patients alive at 12 months from first date of treatment; CCI PFS = Progression-free survival; PFS6, PFS12 = Progression-free survival at 6, 12 months, respectively; CCI
CC1 [REDACTED]; PRAE = Possibly related adverse event; CCI [REDACTED];
RECIST 1.1 = Response Evaluation Criteria in Solid Tumors version 1.1; SAE = Serious adverse event; TL = Target lesion; CCI .

Note: Toxicities will be classified as per CTCAE grading system NCI CTCAE version 5.0. Analysis of ORR and DoR will be based upon Investigator assessment according to RECIST 1.1. Prior irradiated lesions may be considered measurable and selected as TLs providing they fulfill the other criteria for measurability.
Note: An AESI is an AE of scientific and medical interest specific to understanding of the IP. AESIs for durvalumab include, but are not limited to, events with a potential inflammatory or immune-mediated mechanism and which may require more frequent monitoring and/or interventions such as steroids, immunosuppressants, and/or hormone replacement therapy.

Overall design

This is a Phase II open-label, single-arm, multicenter, international study to evaluate the clinical activity of durvalumab in patients with Stage III unresectable NSCLC who are deemed to be ineligible for chemotherapy per Investigator assessment.

Patients will be enrolled into 2 cohorts according to radiotherapy pretreatment dose (Cohort A: standard radiation therapy [60 gray (Gy) \pm 10% or hypofractionated bioequivalent dose (BED)]; Cohort B: palliative radiation therapy [40 to < 54 Gy or hypofractionated BED]). This study will be conducted in Europe and North America.

Study period

Estimated date of first patient enrolled: Q2 2020

Estimated date of last patient completed: Q2 2023

Number of patients

Approximately 102 patients are being treated with durvalumab in this study in Europe and North America. Patients will be in complete response (CR), partial response (PR), or have stable disease (SD) following radiation therapy, as assessed by the Investigator and further supported by the screening imaging radiological assessment. Patients must not have progressed following

radiation therapy, and radiation therapy must be completed within 6 weeks (42 days) prior to first durvalumab administration. The last dose of radiation therapy is defined as the day of the last radiation treatment session.

Approximately 148 patients are screened to achieve 102 patients treated with durvalumab and 60 evaluable patients.

Note: "Screened" means a patient's or their legally acceptable representative's, agreement to participate in a clinical study following completion of the informed consent process. Potential patients who are screened for the purpose of determining eligibility for the study, but are not randomized/assigned in the study, are considered "screen failures", unless otherwise specified by the protocol.

Treatments and treatment duration

All patients will receive 1500 mg durvalumab via intravenous (IV) infusion every 4 weeks (q4w) for 12 months (13 doses/cycles). The last administration of durvalumab will be on week 48 unless there is clinical progression, confirmed radiological progression, unacceptable toxicity, withdrawal of consent, or another discontinuation criterion is met. (Please note: If a patient's weight falls to 30 kg or below, the patient should receive weight-based dosing equivalent to 20 mg/kg of durvalumab q4w after consultation between Investigator and Study Physician, until the weight improves to > 30 kg, at which point the patient should resume the fixed-dosing of durvalumab 1500 mg q4w).

Progression during treatment

During the treatment period, patients who are clinically stable at an initial RECIST 1.1-defined progressive disease (PD) may continue to receive study treatment at the discretion of the Investigator and patient. A follow-up scan is to be collected after the initial RECIST 1.1-defined PD, preferably at the next (and no later than the next) scheduled imaging visit, and no less than 4 weeks after the prior assessment of PD; this follow-up scan is evaluated using the Confirmation of Radiological Progression criteria. Patients with confirmed PD who continue to receive durvalumab at the discretion of the Investigator and patient (following consultation with AstraZeneca) can receive treatment for the remainder of the 12-month treatment period, and tumor assessments should continue on their regular imaging schedule for the duration of treatment.

Follow-up of patients after discontinuation of study drug

Patients who have discontinued study treatment due to toxicity or symptomatic deterioration, clinical progression, or who have commenced subsequent anticancer therapy, will be followed up for adverse events (AEs) and with PRO-questionnaires for 90 days after investigational product (IP) discontinuation, and thereafter followed up with tumor assessments until

RECIST 1.1-defined radiological PD plus an additional follow-up scan or until death (whichever comes first).

Survival

All patients in the study should be followed up for survival at months 2, 3, 4, 6, 8, 10, and 12 following treatment discontinuation or completion, and then every 12 weeks until death, withdrawal of consent, or the end of the study, as per the SoA.

Steering Committee

If required, a Steering Committee (SC) will be assembled by AstraZeneca for the executive oversight and supervision of the study. The SC will consist of oncology experts and a statistician who serve their role through regular scheduled meetings or teleconferences and, if necessary, additional ad hoc meetings. Details of the SC remit, procedures, processes, and meeting frequency will be outlined in an SC Charter.

Interim analysis

No formal interim analyses are planned for this study.

Statistical methods

The primary objective of this study is to assess the safety and tolerability of durvalumab which is defined as Grade 3 and Grade 4 possibly related adverse events (PRAEs), as assessed by the Investigator, observed within 6 months after the initiation of durvalumab treatment. In addition, safety and tolerability of durvalumab will be characterized for the cohorts of patients who received Standard Radiotherapy (60 Gy \pm 10% or hypofractionated BED) and patients who received palliative radiotherapy (40 to < 54 Gy or hypofractionated BED).

Safety data will be summarized descriptively overall, by seriousness, by causality and by maximum National Cancer Institute (NCI) Common Terminology Criteria for Adverse Events (CTCAE) Grade. The exact 95% confidence intervals (CIs) around the incidence of Grade 3 and Grade 4 PRAEs will be reported for patients overall and separately for each cohort.

The median PFS, median OS, and median time to NSCLC-related death, together with their corresponding 95% CIs, will be calculated using Kaplan-Meier product limit methods. The proportion of patients who are progression-free at 6 and 12 months and the proportion of patients who are alive at 12 months will be presented. In addition, the objective response rate (ORR), based on Investigator assessments, together with the corresponding 95% CIs will be reported.

[figure not shown]
A total of approximately 102 patients are treated with the study drug in 2 cohorts: approximately 59 patients in the Standard Radiotherapy Cohort and approximately 43 patients in the Palliative Radiotherapy Cohort. It is estimated that a sample size of a minimum 60 patients would be required to provide an adequate level of confidence in the estimated incidence of Grade 3 and 4

PRAEs occurring within 6 months after initiation of durvalumab treatment, which is the primary endpoint. With a sample size of 60 patients, the exact binomial 95% CI for an observed incidence rate of 12% would be 5% to 23%. If the underlying/true incidence rate was 12% as reported in PACIFIC, on repeated implementations of this study, observing an incidence rate less than 5% or greater than 18.3% would be approximately 5% for each region/tail. Furthermore, if there are 30 patients in each cohort (Standard Radiotherapy and Palliative Radiotherapy) and the true incidence of Grade 3 and Grade 4 PRAEs occurring within 6 months after initiation of durvalumab treatment is 12%, the precision will be approximately $\pm 13.0\%$ (95% CI: 3.1, 29.1) in each cohort.

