5.1 Inclusion criteria

Patients are eligible to be included in the study only if all of the following inclusion criteria and none of the exclusion criteria apply:

Informed consent

- 1 Capable of giving signed informed consent which includes compliance with the requirements and restrictions listed in the informed consent form (ICF) and in this protocol.
- 2 Provision of signed and dated, written ICF prior to any mandatory study specific procedures, sampling, and analyses.
- 3 Provision of signed and dated written genetic ICF prior to collection of sample for genetic analysis (optional).

The ICF process is described in Appendix A 3.

Age

- 4 Age \geq 18 years at the time of screening.

Type of patient and disease characteristics

- 5 Histologically- or cytologically-documented NSCLC with locally-advanced, unresectable Stage III disease (according to the IASLC Staging Manual Version 8 [IASLC 2016]).
 - (a) Imaging to rule out distant metastasis is required.

(b) Endobronchial ultrasound with biopsy is encouraged in patients with suspected lymph node involvement.

6 Deemed ineligible for chemotherapy per Investigator assessment (eg, comorbidities, poor PS, etc).

7 Receipt of radiation therapy that was completed within 42 days prior to first IP dose administration in the study.

8 Patients must have received a total dose of radiation of 40 to 66 Gy (standard or hypofractionated BED). Note that patients will be assigned to Cohort A (standard radiation therapy [60 Gy \pm 10% or hypofractionated BED]) or Cohort B (palliative radiation therapy [40 to < 54 Gy or hypofractionated BED]) based upon total dose of radiation received. Sites are encouraged to adhere to mean organ radiation dosing as follows:

- (a) Mean lung dose < 20 Gy and/or V20 < 35%;
- (b) Mean esophagus dose < 34 Gy;
- (c) Heart V45 < 35% or V30 < 30%. Heart V45 < 35% or V30 < 30%.

Note: Sites should be aware of the recent RTOG 0617 Study data ([Bradley et al 2015](#)) demonstrating that doses higher than 60 Gy may be associated with greater toxicity and worse efficacy.

- (d) Patients with WHO/ECOG PS 2 or chronic lung disease (pulmonary emphysema or chronic obstructive pulmonary disease) must have received a V20 < 25%.

9 Patients must not have progressed following radiation therapy, as per Investigator assessed RECIST 1.1 criteria.

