- (a) Patients with measurable disease and/or nonmeasurable and/or no evidence of disease assessed at baseline by computed tomography (CT)/magnetic resonance imaging (MRI) will be eligible for this study.
- (b) Prior irradiated lesions may be considered measurable and selected as target lesions (TLs) providing they fulfill the other criteria for measurability.

10 WHO/ECOG PS of \leq 2.

11 No prior exposure to immune-mediated therapy including, but not limited to, anti-CTLA-4, anti-PD-1, anti-PD-L1, and antiprogrammed cell death ligand 2 (anti-PD-L2) antibodies, excluding therapeutic anticancer vaccines.

12 Adequate organ and marrow function as defined below:

- Hemoglobin \geq 9.0 g/dL
- Absolute neutrophil count \geq 1.0×10^9 /L
- Platelet count \geq 75×10^9 /L
- Serum bilirubin \leq 1.5 \times the upper limit of normal (ULN). This will not apply to patients with confirmed Gilbert's syndrome, who will be allowed in consultation with their physician.

- Alanine aminotransferase (ALT) and aspartate aminotransferase (AST) $\leq 2.5 \times$ ULN
- Measured creatinine clearance (CL) > 30 mL/min or calculated CL > 30 mL/min as determined by Cockcroft-Gault (using actual body weight).

Males:

$$\text{Creatinine CL} = \frac{\text{Weight (kg)} \times (140 - \text{Age})}{72 \times \text{serum creatinine (mg/dL)}}$$

Females:

$$\text{Creatinine CL} = \frac{\text{Weight (kg)} \times (140 - \text{Age})}{72 \times \text{serum creatinine (mg/dL)}} \times 0.85$$

13 Must have a life expectancy of at least 12 weeks.

Weight

14 Body weight > 30 kg at enrollment and first IP dose administration

Sex

15 Male or female

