- All other lesions, including small lesions (longest diameter < 10 mm or pathological lymph nodes with ≥ 10 mm to < 15 mm short axis diameter at baseline³)
- Truly nonmeasurable lesions include the following: bone lesions, leptomeningeal disease, ascites, pleural/pericardial effusion, inflammatory breast disease, lymphangitic involvement of skin or lung, and abdominal masses/abdominal organomegaly identified by physical examination (manual palpation) that is not measurable by CT or MRI
- Brain metastasis

Special cases:

- Lytic bone lesions or mixed lytic–blastic lesions, with identifiable soft tissue components, can be considered measurable if the soft tissue component meets the definition of measurability. Blastic lesions are considered nonmeasurable.

² The short axis is defined as the longest axis perpendicular to long axis

³ Lymph nodes with < 10 mm short axis diameter are considered nonpathological and should not be recorded or followed as NTLs.

- Cystic metastases can be considered measurable lesions if they meet the criteria for measurability from a radiological point of view, but if noncystic lesions are present in the same patient, these should be selected over cystic lesions as TLs.

Target lesions:

A maximum of 5 measurable lesions (with a maximum of 2 lesions per organ), representative of all lesions involved suitable for accurate repeated measurement, should be identified as TLs at baseline. Lymph nodes, in any location (local/regional and distant), are collectively considered as a single organ, with a maximum of 2 lymph nodes as TLs. A bilateral organ (eg, adrenal glands), a segmented organ (eg, liver), or a multilobed organ (eg, lung) is each considered as a single organ.

A previously irradiated lesion may be selected as a TL provided it fulfills the criteria for reproducible measurability and is the only lesion available.

Tumor lesions selected for fresh screening biopsy should not be selected as TLs, unless imaging occurred at least ~2 weeks after biopsy, allowing time for healing.

Nontarget lesions (NTLs):

Additional measurable lesions not recorded as TLs and nonmeasurable lesions (or sites of disease) should be identified as NTLs at baseline.

Imaging modalities

A summary of the imaging modalities to be used for RECIST 1.1 assessment of TL, NTL, and new lesions is provided in [Table 14](#).

Table 14 Summary of imaging modalities for tumor assessment

Target Lesions	Nontarget Lesions	New Lesions

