#### 1.1.2 Secondary Objectives

Secondary Efficacy Objectives	Endpoints / Variables
To assess the efficacy of durvalumab treatment in terms of progression-free survival (PFS) and overall survival (OS)	Median PFS according to Response Evaluation Criteria in Solid Tumors version 1.1 (RECIST 1.1) as assessed by the Investigator PFS6 and PFS12 according to RECIST 1.1 as assessed by the Investigator Median OS and OS12
To further assess the efficacy of durvalumab treatment in terms of objective response rate (ORR) and duration of response (DoR)	Objective response (OR) according to RECIST 1.1 as assessed by the Investigator DoR according to RECIST 1.1 as assessed by the Investigator
To assess the efficacy of durvalumab treatment in terms of lung cancer mortality	Lung cancer mortality

Secondary Safety Objectives	Endpoints / Variables
To further assess the safety and tolerability profile of durvalumab treatment, including all adverse events (AEs)	AEs, serious adverse events (SAEs), adverse events of special interest (AESIs), immune-mediated adverse events (imAEs), physical examinations, vital signs including blood pressure (BP) and pulse rate, electrocardiograms (ECGs) and laboratory findings including clinical chemistry, haematology and urinalysis

Note: Analysis of OR and DoR will be based upon Investigator assessment according to RECIST 1.1. Prior irradiated lesions may be considered measurable and selected as target lesions provided they fulfil the other criteria for measurability.

[figure not shown]
An AESI is an AE of scientific and medical interest specific to the understanding of durvalumab. AESIs for durvalumab include, but are not limited to, events with a potential inflammatory or immune-mediated mechanism and which may require more frequent monitoring and/or interventions such as steroids, immunosuppressants and/or hormone replacement therapy.

An imAE is defined as an AESI that is associated with drug exposure and is consistent with an immune-mediated mechanism of action and where there is no clear alternate etiology.

[figure not shown]

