### **3.1.1 Site Investigator Assessments Using RECIST 1.1**

#### **3.1.1.1 Target Lesions**

Measurable disease is defined as having at least one measurable lesion, not previously irradiated, which is  $\geq 10$  mm in the longest diameter (LD), (except lymph nodes which must have short axis  $\geq 15$  mm) with CT or MRI and which is suitable for accurate repeated measurements.

A maximum of five measurable lesions (with a maximum of two lesions per organ), representative of all lesions involved and suitable for accurate repeated measurement, should be identified as TLs at baseline. It may be the case that, on occasion, the largest lesion does not lend itself to reproducible measurement. In which circumstance the next largest lesion, which can be measured reproducibly, should be selected. If more than one baseline scan is recorded, then measurements from the one that is closest and prior to initiation of durvalumab will be used to define the baseline sum of TLs.

All other measurable lesions not recorded as TL, and all non-measurable lesions (or sites of disease) should be identified as non-target lesions (NTLs) at baseline. Measurements are not required for these lesions, but their status should be followed at subsequent visits.

For patients who do not have measurable disease at entry (ie, no TLs) but have non-measurable disease, evaluation of overall visit responses will be based on the overall NTL assessment and the absence/presence of new lesions (see Section [3.1.1.3](#) for further details). If a patient does not have measurable disease at baseline, then the TL visit response will be not applicable (NA).

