### **Irradiated Lesions/Lesion Intervention**

A previously irradiated lesion may be selected as a TL, provided that it fulfils the criteria for reproducible measurability and is the only lesion available.

Any TL (including lymph nodes), which has had intervention in addition to study treatment during the study (eg, irradiation / palliative surgery / embolization), should be handled in the following way and once a lesion has had intervention then it should be treated as having

intervention for the remainder of the study noting that an intervention will most likely shrink the size of tumors:

- Step 1: the diameters of the TLs (including the lesions that have had intervention) will be summed and the calculation will be performed in the usual manner. If the visit response is PD this will remain as a valid response category.
- Step 2: If there was no evidence of progression after step 1, treat the lesion diameter (for those lesions with intervention) as missing and if  $\leq 1/3$  of the TLs have missing measurements then scale up as described in the ‘Scaling’ section below. If the scaling results in a visit response of PD then the patient would be assigned a TL response of PD.
- Step 3: If, after both steps, PD has not been assigned, then, if appropriate (ie, if  $\leq 1/3$  of the TLs have missing measurements), the scaled sum of diameters calculated in step 2 should be used, and PR or SD then assigned as the visit response. Patients with intervention are evaluable for CR as long as all non-intervened lesions are 0 (or <10mm for lymph nodes) and the lesions that have been subject to intervention have a value of 0 (or <10mm for lymph nodes) recorded. If scaling up is not appropriate due to too few non-missing measurements, then the visit response will be set as NE.

At subsequent visits the above steps will be repeated to determine the TL and overall visit response. When calculating the previous minimum, lesions with intervention should be treated as missing and scaled up (as per step 2 above).

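### Three rules conflict on whether an irradiated lesion can be a target lesion; depending on the rule, a patient may be unable to have a partial response, or the target-lesion sum may change

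*Protocol*

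**What the plan says.** **Permissive rule.** The notes to the objectives in the protocol synopsis and Section 3 say "Prior irradiated lesions may be considered measurable and selected as TLs providing they fulfill the other criteria for measurability". Inclusion criterion 9(b) in protocol Section 5.1 says the same, as does the note in SAP Section 1.1.2: "Prior irradiated lesions may be considered measurable and selected as target lesions provided they fulfil the other criteria for measurability". SAP Section 2.2.1 repeats criterion 9(b) when it lists the key entry criteria.

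**Only-lesion rule.** Protocol Appendix F, under target lesions, says "A previously irradiated lesion may be selected as a TL provided it fulfills the criteria for reproducible measurability and is the only lesion available". The SAP part headed Irradiated Lesions/Lesion Intervention carries the same condition: "provided that it fulfils the criteria for reproducible measurability and is the only lesion available".

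**Exclusion in the SAP definition.** SAP Section 3.1.1.1 opens with "Measurable disease is defined as having at least one measurable lesion, not previously irradiated". It then sets the target-lesion (TL) visit response to not applicable (NA) for any patient without measurable disease. The definition of measurable in Appendix F has no such exclusion.

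**Population.** Inclusion criterion 7 requires "Receipt of radiation therapy that was completed within 42 days prior to first IP dose administration in the study", and criterion 8 sets a total dose of 40 to 66 Gy. Criterion 5 requires locally advanced Stage III disease, with imaging to rule out distant metastasis.

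**The concern.** Being the only lesion available is not a measurability criterion, so the second rule restricts the first, and the SAP definition is stricter than both. The three cannot all be followed. In many trials this would be a marginal matter. Here all patients have just been irradiated for localised disease, so irradiated lesions are plausibly the usual candidates for TL status (an inference, since no lesion counts are given).

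Visit responses are derived by program from target lesions, non-target lesions and new lesions. ORR, best objective response, duration of response and progression-free survival (PFS) all depend on that derivation. If the rule is unsettled, a reader cannot tell whether these results reflect the tumours or the passage that was applied.

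**Working it through.** The plan gives no expected ORR, no precision for it and no count of patients by lesion type, so there is no plan figure to reproduce. The check compares the rules, follows them through SAP Table 4, and then shows a range.

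**Step 1. TL status under each rule.**

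| Baseline lesions | Permissive rule | Only-lesion rule, literal | Only-lesion rule, read as no unirradiated lesion available | SAP definition of measurable disease |
|---|---|---|---|---|
| A single lesion, irradiated | TL | TL | TL | Not measurable disease; TL = NA |
| Two or more lesions, all measurable ones irradiated | TLs | No TL; TL = NA | TLs | Not measurable disease; TL = NA |
| An unirradiated and an irradiated measurable lesion | Both may be TLs | Unirradiated lesion only | Unirradiated lesion only | Measurable disease present; status of the irradiated lesion not settled |

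**Step 2. From TL status to overall response.** I enumerated every combination of target, non-target and new-lesion status in SAP Table 4. PR arises only when the TL response is CR or PR. With TL = NA the possible results are CR, SD, NE, no evidence of disease (NED) or PD, never PR. SAP Section 3.3.3 defines ORR over the Safety Analysis Set, so such a patient stays in the denominator. Radiological PD then needs a new lesion or unequivocal non-target progression, which is how PFS is affected.

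**Step 3. Two hypothetical patients.**

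- *All measurable lesions irradiated.* Primary 40 mm and node 20 mm, sum 60 mm. They shrink to 26 and 16 mm, sum 42 mm; 42/60 − 1 = −30.0%. With both as TLs this is PR, subject to the confirmation that SAP Section 3.3.3 requires. With TL = NA and non-target disease persisting, it is SD. The example sits exactly on the 30% threshold.
- *Irradiated primary 40 mm, unchanged, plus an unirradiated 12 mm lesion.* If the small lesion falls to 8 mm, both as TLs gives 48/52 − 1 = −7.7%, SD. The small lesion alone gives 8/12 − 1 = −33.3%, PR if non-target disease has not progressed. If instead it grows by 5 mm (the absolute threshold for PD), both as TLs gives 5/52 = +9.6%, SD. Alone it gives 5/12 = +41.7%, PD.

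The second patient shows that even the looser reading can move a patient between categories, in either direction.

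**Step 4. Range for ORR.** Let f be the share of patients who would otherwise have TLs but are left without them, and r the response rate with TLs. Ignoring CR through non-target lesions, ORR = (1 − f) × r. Inputs: N = 102 (protocol Section 9.2); r = 28.4%, the durvalumab response rate quoted in protocol Section 2.3.1 for a different population, used as an assumption; f not given anywhere, so taken over its whole range. The intervals are exact Clopper-Pearson at the rounded count.

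| f | ORR | Count | 95% CI |
|---|---|---|---|
| 0 | 28.4% | 29/102 | 19.9–38.2 |
| 10% | 25.6% | 26/102 | 17.4–35.1 |
| 25% | 21.3% | 22/102 | 14.0–30.8 |
| 50% | 14.2% | 14/102 | 7.7–22.0 |
| 75% | 7.1% | 7/102 | 2.8–13.6 |
| 100% | 0% | 0/102 | 0–3.6 |

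With r = 20% or 40%, the f = 50% row becomes 10.0% or 20.0%. This shows sensitivity only; it does not estimate the effect in this trial.

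**The case against.** The strongest reply is that the only-lesion wording is naturally read as allowing irradiated lesions when no unirradiated one is available. On that reading, patients whose measurable lesions were all irradiated keep their TLs and nobody loses the chance of PR. That is right for the comparison between the first two rules. It does not remove the change in the TL sum shown above, and it does not touch the SAP definition of measurable disease.

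Second, protocol Section 8.1 sends assessors to Appendix F, whereas 9(b) is an eligibility note. A reader might infer that sites have been choosing TLs by different rules. That is possible, but nothing in the documents shows it. A reader might also infer that a site would take just one of two irradiated lesions as the TL. No rule says that, and Appendix F asks for TLs that represent all the lesions involved.

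Third, SAP Table 2 gives NA when no TLs are recorded at baseline, and SAP Section 3.1.1.1 equates no measurable disease with no TLs. A programmer could therefore work from the recorded TLs and never apply the irradiation exclusion. That is a sensible outcome, but the SAP does not say so.

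Finally, patients without measurable disease are eligible by design, so some cannot have a PR under any rule. The study is single-arm and descriptive with a safety primary endpoint. Both points stand and limit the weight of the finding.

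**Conclusion.** The conflict is real, is in the current text of both documents, and should be resolved. Loss of PR follows from the SAP definition of measurable disease, or from the literal only-lesion reading when a patient has two or more irradiated lesions. Under the looser reading the consequence is a different TL sum, which can change a PR or PD call.

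A reader might conclude that many patients cannot have a PR, or put a number of ORR points on the loss. The documents support neither. They give no lesion counts, the effect on ORR starts at zero, and any upper figure rests on an assumed share of patients. The effects are confined to ORR, best objective response, duration of response and PFS. The primary endpoint, Grade 3 and 4 possibly related adverse events, is not affected.

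**What to change.** State one rule wherever the matter appears: the protocol synopsis, Section 3, Section 5.1 and Appendix F, and SAP Sections 1.1.2, 2.2.1 and 3.1.1.1 with its part on irradiated lesions. The permissive rule already stands in the objectives notes and criterion 9(b) of both documents, so the smallest edit is two deletions:

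- the closing only-lesion condition in Appendix F and in the SAP irradiated-lesion paragraph;
- the words after the comma in "Measurable disease is defined as having at least one measurable lesion, not previously irradiated".

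Removing either one alone leaves a conflict.

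In the SAP, also:

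- say that TLs recorded by the investigator are analysed as TLs whatever their irradiation status;
- report how many patients had no TL and how many had only irradiated TLs, using the radiotherapy treated location listed in SAP Section 3.5.1;
- add ORR among patients with TLs at baseline as a supportive analysis.

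The cost is a few edits, one flag and one extra table, with no new data collection. The limit is timing. The text already describes about 102 patients as treated and the latest SAP changes are dated January 2024, so most baselines have probably been recorded and cannot be re-selected. No field described in the documents shows which rule a site followed. The gain is therefore mainly in the SAP derivation and in transparent reporting.
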